#### 4.4.1.3 Supportive Analyses

As a sensitivity analysis, the change from Baseline in Schiff sensitivity score at Week 12 will be compared between study products (test toothpaste vs. negative control) using an Analysis of Covariance (ANCOVA) model with study product as a fixed effect and Baseline Schiff sensitivity score as a covariate.

Using the above model, adjusted mean change from Baseline, along with 95% CIs will be reported by study product. P-values testing for non-zero change from Baseline will be presented for all study products. Mean difference between study products (test toothpaste vs. negative control), 95% CIs and p-values will be provided for Schiff sensitivity score in Table 14.2.2.1.3. Significance testing will be conducted at the two-sided 5% significance level.

If there is more than 10% difference in the overall number of subjects between PP and mITT populations, a summary and analysis of the primary efficacy variable (MMRM and ANCOVA) will be presented for the PP population in Table 14.2.2.2.1, Table 14.2.2.2.2 and Table 14.2.2.2.3, respectively.

#### 4.4.2 Secondary Efficacy Endpoints

The mITT population will be considered as the primary population for efficacy analyses.

GlaxoSmithKline Consumer Healthcare Confidential Statistical Analysis Plan Template v6.0 Page **19** of **36** 

#### 4.4.2.1 Change from Baseline in Schiff Sensitivity Score

The secondary efficacy variable is the change from Baseline in Schiff sensitivity score at Week 6 (for the comparisons between test product and negative control and between positive control and negative control) and Week 12 (for the comparison between positive control and negative control only), derived as the average score of the 2 test teeth (identified at Baseline). The change from Baseline is derived from the individual teeth first before calculating the average change of the 2 test teeth.

Individual data for Schiff sensitivity score will be listed for each subject by study product group and visit in Listing 16.2.6.1 for all randomized subjects.

#### 4.4.2.1.1 Statistical Hypothesis, Model and Method of Analysis

Two comparisons will be considered for this secondary endpoint. Firstly, the comparison between the test toothpaste and the negative control at Week 6 in the mITT population. Secondly, the comparison between the positive control and the negative control at Week 6 and Week 12 in the mITT population.

- 1. Study product differences will be tested under the null hypothesis at Week 6:
- H0: there is no difference between test product and negative control;
- H1: there is a difference between test product and negative control;
- 2. Study product differences will be tested under the null hypothesis at Week 6 and Week 12:
- H0: there is no difference between positive control and negative control;
- H1: there is a difference between positive control and negative control;

The results for this endpoint will be obtained from the MMRM detailed in Section 4.4.1.2. The same statistics as presented for the Week 12 analysis for test toothpaste compared to negative control (see Section 4.4.1.2) will also be presented for the Week 6 analysis for test toothpaste compared to negative control, and for the Week 6 and Week 12 analysis for positive control compared to negative control in Table 14.2.2.1.2.

#### 4.4.2.1.2 Supportive Analyses

As a sensitivity analysis, the change from Baseline in Schiff sensitivity score at Week 6 and Week 12 will be compared between study products (test toothpaste vs. negative control [Week 6] and positive control vs. negative control [Week 6 and 12]) using a separate ANCOVA model for each week with study product as fixed effect and Baseline Schiff sensitivity score as a covariate. The comparison for positive control vs. negative control at Week 12 will be obtained from the results of the same ANCOVA detailed in section 4.4.1.3.

GlaxoSmithKline Consumer Healthcare Confidential CCI Statistical Analysis Plan Template v6.0 Page 20 of 36

Using the above model, adjusted mean change from Baseline, along with 95% CIs will be reported by study product. P-values testing for non-zero change from Baseline will be presented for all study products. Mean difference between study products (test toothpaste vs. negative control and positive control vs. negative control), 95% CIs and p-values will be provided for Schiff sensitivity score in Table 14.2.2.1.3. Significance testing will be conducted at the two-sided 5% significance level.

## 4.4.2.2 Change from Baseline in Tactile Threshold

The secondary efficacy variable is the change from Baseline in Tactile Threshold (g) at Week 6 and Week 12, derived as the average value of the 2 test teeth (identified at Baseline). The change from Baseline is derived from the individual teeth first before calculating the average change of the 2 test teeth. The teeth recorded as >80 g (for post baseline) will be set to 90g, in calculation of average tactile threshold (g) and change from Baseline.

Descriptive statistics (n, missing, mean, SD, SE, median, minimum, and maximum) will be presented for Tactile Threshold (g) calculated as the average score of the 2 test teeth at each assessment time point together with the change from Baseline in Table 14.2.3.1.1 for all subjects in the mITT population by study product. Raw means ( $\pm$  SE) of the Tactile Threshold (g) at each time point will be plotted by study product in Figure 14.2.3.1.4 for all subjects in the mITT population.

Individual data for Tactile Threshold (g) will be listed for each subject by study product group and visit in Listing 16.2.6.2 for all randomized subjects.

## 4.4.2.2.1 Statistical Hypothesis, Model and Method of Analysis

Two comparisons will be considered for this secondary endpoint. Firstly, the comparison between the test toothpaste and the negative control in the mITT population. Secondly, the comparison between the positive control and the negative control in the mITT population.

- 1. Study product differences will be tested under the null hypothesis at Week 6 and Week 12:
- H0: there is no difference between test product and negative control;
- H1: there is a difference between test product and negative control;
- 2. Study product differences will be tested under the null hypothesis at Week 6 and Week 12:
- H0: there is no difference between positive control and negative control;
- H1: there is a difference between positive control and negative control;

GlaxoSmithKline Consumer Healthcare Confidential Statistical Analysis Plan Template v6.0 Page **21** of **36** 

Change from Baseline in tactile threshold (g) will be analyzed using the same MMRM as the primary endpoint but with Baseline tactile threshold (g) as a covariate, rather than Baseline Schiff sensitivity score. In addition, the maximum Baseline Schiff sensitivity score of the two test teeth (2 or 3) will be fitted as a fixed effect.

Using the above model, adjusted mean change from Baseline, along with 95% CIs will be reported by study product. P-values testing for non-zero change from Baseline will be presented for both study products. Mean difference between study products, 95% CIs and p-values will be provided for Tactile Threshold (g) score in Table 14.2.3.1.2. Significance testing will be conducted at the two-sided 5% significance level.

The assumption of normality and homogeneity of variance in the MMRM will be investigated. In case of violation of these assumptions, a suitable non-parametric test (the Van Elteren test, adjusted for the randomization stratification) will be performed to assess change from Baseline comparisons (test toothpaste vs. negative control and positive control vs. negative control at Weeks 6 and 12) and the results will be provided to support the MMRM results; the non-parametric results will be considered to supersede the MMRM results under the observation of strong violations of the assumptions.

#### 4.4.2.2.2 Supportive Analyses

As a sensitivity analysis, the change from Baseline in tactile threshold (g) at Week 6 and Week 12 will be compared between study products (test toothpaste vs. negative control and positive control vs. negative control) using a separate ANCOVA model for each week with study product and the maximum Baseline Schiff sensitivity score of the two test teeth (2 or 3) as fixed effects and the Baseline tactile threshold (g) as a covariate.

Using the above models, adjusted mean change from Baseline, along with 95% CIs will be reported by study product. P-values testing for non-zero change from Baseline will be presented for all study products. Mean difference between study products, 95% CIs and p-values will be provided for Tactile Threshold (g) score in 14.2.3.1.3. Significance testing will be conducted at the two-sided 5% significance level.

If there is more than 10% difference in the overall number of subjects between PP and mITT populations, a summary and analysis of the primary efficacy variable (MMRM and ANCOVA) will be presented for the PP population in Table 14.2.3.2.1, Table 14.2.3.2.2 and Table 14.2.3.2.3, respectively.

#### 4.4.2.3 Change from Baseline in Visual Analogue Scale

The secondary efficacy variable is the change from Baseline in VAS (mm) score at Week 6 and Week 12, derived as the average score or value, respectively, of the 2 test teeth (identified at Baseline). The change from Baseline is derived from the individual teeth first before calculating the average change of the 2 test teeth.

GlaxoSmithKline Consumer Healthcare Confidential Statistical Analysis Plan Template v6.0 Page 22 of 36

Descriptive statistics (n, missing, mean, SD, SE, median, minimum, and maximum) will be presented for VAS (mm) score calculated as the average score of the 2 test teeth at each assessment time point together with the change from Baseline in Table 14.2.4.1.1 for all subjects in the mITT population by study product. Raw means ( $\pm$  SE) of the VAS (mm) score at each time point will be plotted by study product in Figure 14.2.4.1.4 for all subjects in the mITT population.

Individual data for VAS (mm) will be listed for each subject by study product group and visit in Listing 16.2.6.3 for all randomized subjects.

## 4.4.2.3.1 Statistical Hypothesis, Model and Method of Analysis

Two comparisons will be considered for this secondary endpoint. Firstly, the comparison between the test toothpaste and the negative control in the mITT population. Secondly, the comparison between the positive control and the negative control in the mITT population.

- 1. Study product differences will be tested under the null hypothesis at Week 6 and Week 12:
- H0: there is no difference between test product and negative control;
- H1: there is a difference between test product and negative control;
- 2. Study product differences will be tested under the null hypothesis at Week 6 and Week 12:
- H0: there is no difference between positive control and negative control;
- H1: there is a difference between positive control and negative control;

Change from Baseline in VAS (mm) will be analyzed using the same MMRM as mentioned in Section 4.4.2.2.1 but with Baseline VAS (mm) as a covariate, rather than the Baseline tactile threshold (g).

Using the above model, adjusted mean change from Baseline, along with 95% CIs will be reported by study product. P-values testing for non-zero change from Baseline will be presented for both study products. Mean difference between study products, 95% CIs and p-values will be provided for VAS (mm) score in Table 14.2.4.1.2. Significance testing will be conducted at the two-sided 5% significance level.

The assumption of normality and homogeneity of variance in the MMRM will be investigated. In case of violation of these assumptions, a suitable non-parametric test (the Van Elteren test, adjusted for the randomization stratification) will be performed to assess change from Baseline comparisons (test toothpaste vs. negative control and positive control vs. negative control at Weeks 6 and 12) and the results will be provided to support the MMRM results; the

> GlaxoSmithKline Consumer Healthcare Confidential Statistical Analysis Plan Template v6.0 Page 23 of 36

non-parametric results will be considered to supersede the MMRM results under the observation of strong violations of the assumptions.

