## 1.4 Sample Size Calculation

Sufficient subjects will be screened to randomize approximately 240 subjects to study treatment to ensure approximately 235 complete the study (approximately 94 subjects each for test toothpaste and negative control, and 47 subjects for positive control), allowing for 2% dropouts after randomization, as observed in previous clinical studies conducted in China.

The study will be powered sufficiently to demonstrate statistical superiority of the test toothpaste compared to the negative control for the change from Baseline in the Schiff sensitivity score after 12 weeks of treatment.

GlaxoSmithKline Consumer Healthcare Confidential Statistical Analysis Plan Template v6.0 Page 11 of 36

The true effect size is expected to be 0.5 (effect size (ES) = mean difference [test toothpaste – negative control] / pooled standard deviation [SD]; mean difference = 0.3, SD = 0.6). Such assumptions would also infer at least a 15% superior relative mean change from Baseline for the test toothpaste compared to the negative control (assuming mean change from a Baseline Schiff sensitivity score for negative control less than 2), a requirement of the Chinese MoH guidelines for the testing of functional (desensitising) toothpastes for at least one clinical DH measure (Ministry of Health (China), 2010).

With 94 subjects per group (for test toothpaste and negative control arms), there is 92.65% power to detect an effect size of 0.5 at the two-sided 5% significance level based on a two-sample t-test (using PASS software version 19.0.1).

Estimates of the above dropout rate and SD are based on results from three similar clinical studies (sponsor clinical studies: 205794, 208153, 216954).

The positive control has clinically proven longer-term DH efficacy in two clinical studies conducted in China on Chinese populations (sponsor clinical studies: **CC**) which satisfied the China MoH requirements (Ministry of Health (China), 2010). As such, it has been included in this study as a benchmark of performance in the Chinese population for 'study validation'; 47 subjects in the positive control group are deemed sufficient to demonstrate statistical superiority for positive vs. negative controls.

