## 4.4.1.2 Statistical Hypothesis, Model, and Method of Analysis

The primary comparison is between the test toothpaste and the negative control in the mITT population. As there is only a single primary objective no adjustment for multiple comparisons is required.

Study product differences will be tested under the null hypothesis at Week 12:

- H0: there is no difference between test product and negative control;
- H1: there is a difference between test product and negative control;

GlaxoSmithKline Consumer Healthcare Confidential Statistical Analysis Plan Template v6.0 Page 18 of 36

Change from Baseline in Schiff sensitivity score will be analyzed using a Mixed Model with Repeated Measures (MMRM), with study product, visit and study product by visit interaction as fixed effects, and Baseline Schiff sensitivity score as a covariate. Subject will be included as a repeated measure with unstructured covariance matrix. Kenward Rogers degrees of freedom approach will be applied (Kenward and Roger, 1997). If the model with unstructured covariance matrix does not converge then compound symmetry covariance matrix will be used.

Using the above model, adjusted mean change from Baseline, along with 95% confidence intervals (CIs) will be reported by study product. P-values testing for non-zero change from Baseline will be presented for all study products. Mean difference between study products at Week 12 (test toothpaste compared to negative control), 95% CIs and p-values will be provided for Schiff sensitivity score in Table 14.2.2.1.2. Significance testing will be conducted at the two-sided 5% significance level.

The assumption of normality and homogeneity of variance in the MMRM will be investigated. In case of violation of these assumptions, a suitable non-parametric test (the Van Elteren test, adjusted for the randomization stratification) will be performed to assess change from Baseline comparisons (test toothpaste vs. negative control at Week 12) and the results will be provided to support the MMRM results. The non-parametric results will be considered confirmatory under the observation of strong violations of the assumptions.

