#### 4.4.3 Handling of Missing Values/Censoring/Discontinuations

Missing data will not be replaced or imputed. Subjects who withdraw from the study prematurely will be included in the statistical analyses up to the point of discontinuation.

MMRM analyses account for missing data using 'a missing at random' assumption, i.e., there is a systematic relationship between the propensity for missing values and the observed data, but not the missing data. Under such assumptions, MMRM is shown to provide unbiased estimates of the treatment effect, whilst the analysis of only complete cases using ANCOVA are biased (Baron et al, 2008; Ashbeck et al, 2016). Such complete case analysis requires a 'missing completely at random' assumption to remain unbiased and this is unlikely to hold, i.e., the fact that the data are missing is independent of the observed and unobserved data.

Using an MMRM, it will therefore be assumed that a subject with missing data at one post-Baseline visit would have obtained a similar efficacy result at that visit compared to a subject using the same study product with similar non-missing results at other timepoints (Baseline and the other post-Baseline visit).

Sensitivity analyses will present results from the separate ANCOVA models using only nonmissing values at each single time point. Additional sensitivity analyses may be added to the SAP prior to unblinding in case of high drop-out rates and/or exclusion from PP population.

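### The rank test that would supersede the VAS MMRM leaves out Baseline VAS, for which both planned VAS models adjust

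*SAP*

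**What the plan says.** Every planned parametric model adjusts for the Baseline value of its own measure. For VAS, the MMRM (SAP 4.4.2.3.1) and the ANCOVA (SAP 4.4.2.3.2) both carry Baseline VAS as a covariate and the maximum Baseline Schiff score as a fixed effect.

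The only named fallback is this: "a suitable non-parametric test (the Van Elteren test, adjusted for the randomization stratification) will be performed to assess change from Baseline". The randomization stratification is a single two-level factor, the maximum Baseline Schiff score of the two test teeth (SAP 3.2). The fallback covers test versus negative control and positive versus negative control, at Weeks 6 and 12.

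Its standing depends on how badly the assumptions fail. It first supports the MMRM. For tactile threshold, SAP 4.4.2.2.1 then says "the non-parametric results will be considered to supersede the MMRM results under the observation of strong violations of the assumptions", and the VAS section has the same rule. For the primary Schiff endpoint, SAP 4.4.1.2 says "The non-parametric results will be considered confirmatory under the observation of strong violations of the assumptions". Protocol 12.3.2 asks only for a suitable non-parametric test adjusted for the stratification. Neither document plans a rank method that adjusts for Baseline.

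**The concern.** If the VAS data force the switch, the deciding analysis drops a covariate that the sponsor thought worth including in both VAS models. Baseline VAS can differ widely within a Schiff stratum: each test tooth needs at least 40 mm on a 100 mm scale. Protocol 4.2 warns that qualifying values may be random highs that later fall back towards the mean. In that situation the change from Baseline depends on Baseline, and subtracting Baseline does not remove the dependence.

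Two things are at stake. The superseding test may use the data less efficiently than another rank test that is equally free of the normality assumption. And part of any chance difference between arms in Baseline VAS would pass into the comparison.

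**Working it through.** **Inputs from the documents.** 94 subjects each on test and negative control (SAP 1.4); for VAS, "Significance testing will be conducted at the two-sided 5% significance level"; two strata; Baseline VAS 40 to 100 mm; planned Schiff values "mean difference = 0.3, SD = 0.6".

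**Assumed, because the documents give no VAS figures.** Baseline VAS truncated to 40-100 mm with SD about 12.5 mm; Week 12 SD about 20 mm; right-skewed (gamma) errors; true difference 8 mm; slope *b* of Week 12 VAS on Baseline VAS varied from 0 to 1.

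**1. The plan's own power.** SAP 1.4 states that "there is 92.65% power to detect an effect size of 0.5 at the two-sided 5% significance level based on a two-sample t-test". Effect size 0.3/0.6 = 0.5; noncentrality 0.5 × √(94/2) = 3.43; 186 degrees of freedom; power 92.65%, as stated. A rank test on raw change has relative efficiency 3/π = 0.955 on normal data, so noncentrality 0.5 × √(47 × 0.955) = 3.35 and power about 91.5%. The stated power concerns Schiff and an unadjusted test. There is no VAS power claim to contradict.

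**2. Why raw change still depends on Baseline.** Within a stratum write Week 12 = a + *b*·Baseline − δ·(test) + error. Then change = a − (1 − *b*)·Baseline − δ·(test) + error. Its variance is (1 − *b*)²·12.5² + σₑ². After adjustment for Baseline it is σₑ² alone, with σₑ² = 20² − *b*²·12.5².

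- *b* = 0: 556.25 against 400, ratio 0.72
- *b* = 0.4: 431.25 against 375, ratio 0.87
- *b* = 0.8: 306.25 against 300, ratio 0.98
- *b* = 1: equal

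**3. Simulated power under these assumptions.**

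| Slope *b* | Van Elteren on raw change | Stratified rank ANCOVA | Gap (points) |
|---|---|---|---|
| 0 | 74% | 85% | 11 |
| 0.2 | 81% | 87% | 6 |
| 0.4 | 85% | 90% | 5 |
| 0.6 | 91% | 92% | 1 |
| 0.8 | 96% | 96% | 0 |
| 1.0 | 98% | 98% | 0 |

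Two further runs of this scenario (1,500 and 2,000 trials per setting) gave gaps of 11, 6, 3, 2, 0 and 12, 8, 6, 2, 0 points at slopes 0 to 0.8. Both tests had size near 5%. On normal data with effect size 0.5, the analytic loss is 0, about 2 and about 5.5 points when Baseline and change correlate at 0, 0.3 and 0.5. At *b* = 0 the assumed VAS values imply 12.5/√556.25 = 0.53.

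**4. Chance imbalance.** The standard error of the between-arm difference in mean Baseline VAS is 12.5 × √(2/94) = 1.8 mm, before any balance gained from stratification. A one-standard-error imbalance shifts the raw-change comparison by (1 − *b*) × 1.8 mm: 1.8 mm at *b* = 0 (1.8/8 = 23% of the effect), 1.1 mm at *b* = 0.4, and nothing at *b* = 1.

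Over all randomizations, the type I error of the raw test stayed at 4.9-5.3% on normal data. Given a Baseline imbalance of 0.2 SD (probability of at least that much about 17%), it was 6.1% and 7.5% at Baseline-change correlations of 0.3 and 0.5. Given 0.3 SD (about 4%), it was 7.3% and 13.9%. Adjusted tests stayed at about 5%.

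**5. The other two endpoints.** In Stratum 1 both teeth score 2, so Baseline average Schiff is exactly 2.0 for everyone and there is nothing to adjust for. In Stratum 2 it is 2.5 or 3.0. Simulated gains for Schiff were 0 to 3 points (for example 79% against 81%). Tactile Baseline is at most 20 g in 10 g steps. Tactile was not simulated, and little gain is expected.

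**The case against.** The strongest reply is that the planned test is valid, pre-specified and consistent with the protocol. It analyses change, which already subtracts Baseline, and it is stratified on a score given for the same air stimulus as VAS. It decides nothing unless violations are strong, and VAS is a secondary endpoint with no part in the success criterion. The adjusted MMRM and ANCOVA are still reported and Baseline VAS is tabulated by product, so an imbalance would be visible. The 11-point gap needs Week 12 VAS to be unrelated to Baseline VAS on the same teeth, which is an extreme case. All of this stands and limits the size of the point. None of it shows a loss from adding Baseline VAS to the rank test.

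Three stronger readings are tempting, and the documents do not support them.

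- **That switching to Van Elteren costs power against the planned model.** In the skewed VAS setting, Van Elteren against Baseline-adjusted ANCOVA gave 74% vs 78%, 79% vs 77%, 85% vs 79%, 91% vs 84% and 95% vs 88% at Baseline-to-Week-12 correlations of 0, 0.12, 0.23, 0.35 and 0.47. Under the kind of departure that triggers the switch, the fallback usually gains on the parametric analysis. The loss is against an adjusted rank test only.
- **That the primary analysis is seriously affected.** The strata already carry most of the Schiff covariate.
- **That the fallback is undermined by missing data**, because SAP 4.4.3 says of complete cases "Such complete case analysis requires a 'missing completely at random' assumption to remain unbiased and this is unlikely to hold". A rank ANCOVA would also use only observed subjects, and planned dropout is 2%.

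**Conclusion.** The point holds for VAS. The superseding rank test in SAP 4.4.2.3.1 omits Baseline VAS and so gives up some efficiency whenever change depends on Baseline. The loss against a stratified rank ANCOVA is 0 to about 11 points of power under the assumed SDs, skewness and 8 mm effect. It is largest if Week 12 VAS is unrelated to Baseline and vanishes if it tracks Baseline closely. The documents do not give that relation, so the loss cannot be pinned down further.

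Protection against a chance Baseline VAS imbalance is partial, not absent. A reader might infer that the test has no guard or an inflated error rate. Stratification helps, and the unconditional error rate is about 5%. Only the error rate conditional on an imbalance rises. For Schiff and tactile the same change is optional. This is a free or cheap improvement, not a fault in validity.

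**What to change.** In SAP 4.4.2.3.1, name a stratified rank ANCOVA as the non-parametric test that supersedes the VAS MMRM under strong violations. Possible wording: *For each comparison and visit, change in VAS and Baseline VAS will be ranked within each maximum Baseline Schiff stratum; ranked change will be regressed on ranked Baseline VAS, and the residuals will be compared between products with a rank test stratified by maximum Baseline Schiff. The Van Elteren test on unadjusted change will be reported alongside.* The last sentence is optional.

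The method remains a non-parametric test adjusted for the stratification, so it fits Protocol 12.3.2 as written. SAP 4.4.1.2 and 4.4.2.2.1 can stay as they are, or follow for uniformity. The change must be in the SAP before the randomization codes are released.

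The cost is one or two sentences and a few lines of code, with no new data or subjects. The downside is a slightly less standard test.
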